#### 9.7.2.2 *Incidence examination*

The cumulative incidence proportion, rate and time to onset of NDD, including ASD will be calculated as well as cumulative incidence proportion for composite CM endpoint and specific CM target body system organ groups based on ICD-10 codes. These statistics will be presented for each overall cohort and separately for offspring *paternally exposed to valproate or lamotrigine/ levetiracetam (composite and separately) in monotherapy 3 months prior to LMP2*.

The cumulative incidence (risk) of the primary outcomes reported each year will be explored by estimating the cumulative incidence of incident reports (plus 95% CI). For purposes of this analysis the denominator is defined according to the population initially at risk at the beginning of the study, since the estimates are cumulative; that is live births for NDD, including ASD and live plus non-live births for CM. The numerator will comprise of counts of incident events as recorded during each year and summed to reflect the cumulative count for all years up to that point. The cumulative incidence proportion will be calculated according to the formula:

$$\left( \frac{\text{Total number of offspring paternally exposed with newly diagnosed outcome during each cumulative year of interest}}{\text{Population initially at risk}} \right) \times 100$$

For each exposure group, the numerator for each year will contain the number of offspring for whom the incident outcome has been recorded in that year and will exclude offspring who have had an outcome previously, within the study period. The denominator will include offspring within the numerator and also offspring who did not have an outcome recorded in the current year or preceding years (i.e. only the ‘at risk’ population will be considered).

The cumulative incidence rate of the primary outcome will be modelled using survival methods and expressed as number of cases per 1000 patients-years at risk (+95%CI). Data may also be stratified according to other relevant strong risk factors for events of interest (age, gender) and stratum-specific incidence rates examined.

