### **9.7.3.2.1 Effect estimation - Neurodevelopmental disorders, including autism**

A crude and a propensity-score (PS) weighted (section 9.7.3.2.3) Cox PH regression model will be used to estimate the HR of NDD, including ASD, with 95% CI (using offspring's calendar age in years as the underlying timescale) in offspring paternally exposed to valproate monotherapy within 3 months prior to LMP2 date compared to the reference group comprised of offspring paternally exposed to lamotrigine or levetiracetam (composite monotherapy) in the same time period. Inclusion of covariates not retained in the PS (section 9.7.3.2.2), in the Cox PH model will be considered in the event of imbalance in prognostically important variables. Covariates measured after index date will be included as time dependent in the Cox PH model, as appropriate. Post-estimation model diagnostics will be undertaken for each final parsimonious model, including log-log plots and Schoenfeld residuals, to assess the proportionality assumption.

Multiple offspring per father is possible and will introduce within-family dependencies into the data. Therefore in the analyses, paternal clustering will be taken into account by correcting standard errors with sandwich estimators (38). For purposes of the primary objective analysis for which the study is powered, a first Cox PH model will be estimated irrespective of clusters classification (section 9.3.1.3). This approach has the limitation to ignore intensity of exposure in the two exposure groups. To overcome this limitation, the first model will be repeated including the exposure intensity variable (estimated based on clusters as by application of k-means methodology (section 9.3.1.3)) as an effect modifier, i.e. the interaction exposure\*k-means will be included in the model. This second approach has the advantage of providing an estimate of the effect of paternal exposure to valproate vs the comparator group stratified by exposure intensity as measured by the k-means clusters.

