5. *Simple pairwise comparison valproate vs lamotrigine and valproate vs levetiracetam in monotherapy.* Valproate, lamotrigine and levetiracetam are medications with similar indications but that may be systematically prescribed for different type of epilepsy (such as valproate for genetically determined epilepsy and lamotrigine for focal onset epilepsy) and potentially other indications (lamotrigine might be prescribed for bipolar disorder and levetiracetam is not). Moreover, they were licensed in different periods (levetiracetam since 2000; lamotrigine since early 1990s; and valproate since 1967 to

treat epilepsy and since 1995 to treat bipolar disorder) resulting in systematic different in the treated populations. With the objective to evaluate if there is a differential effect of using one or the other comparator, a supplementary analysis will be provided to contrast valproate paternal exposure to separately lamotrigine and levetiracetam paternal exposure for the purpose of both NDD and CM outcome:

- a. Describe the characteristics of mother, father and offspring for both the primary and secondary outcome cohort and separately for paternal monotherapy exposure to individual AEDs (valproate or lamotrigine or levetiracetam).
  - b. Investigate the risk of NDD, including ASD, in offspring paternally exposed to valproate (monotherapy), compared to lamotrigine (monotherapy) treatment at the time of conception.
  - c. Investigate the risk of NDD, including ASD, in offspring paternally exposed to valproate (monotherapy), compared to levetiracetam (monotherapy) treatment at the time of conception.
  - d. Investigate the risk of CM, in offspring paternally exposed to valproate (monotherapy), compared to lamotrigine (monotherapy) treatment at the time of conception, in Norway and Denmark only.
  - e. Investigate the risk of CM, in offspring paternally exposed to valproate (monotherapy), compared to levetiracetam (monotherapy) treatment at the time of conception, in Norway and Denmark only.

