  - a. In order to account for potential differences in the association between the cumulative exposure and the outcome at study between different treatments, an interaction term of the continuous variable representing the cumulative exposure and the dichotomous variable representing the valproate or lamotrigine/levetiracetam group will be tested for in each logistic and Cox PH model.
  - b. The cumulative exposure variable will also be categorised empirically according to tertiles of the distribution to represent low, medium and high exposure to each of the three treatment groups separately, since the cumulative exposure pattern may be different for each treatment, plus thresholds cannot be defined a priori as cut-off points are not available by previous literature. For each exposure group (valproate, lamotrigine and levetiracetam) separately, a within-group analysis will be performed to study the dose-response relationship for each outcome by comparing high and medium exposure to treatment against low exposure to treatment as the referent category.
  - c. For each outcome, a pre-defined list of covariates based on final models of primary comparative analyses will be forced into each of the aforementioned logistic and Cox PH model to provide estimates adjusted for relevant confounders. Since the distribution of cumulative exposure and of relevant confounders within each exposure group could differ from those of the other exposure groups, the results from the three within-exposure group analyses for each outcome will not be comparable.
11. *Narrow case definition for primary outcome - NDD*: This sensitivity analysis will use a narrow NDD composite case definition according to the following ICD-10 codes:

Clinical Code Description	ICD-10
Intellectual disability - mild	F70
Intellectual Disability - Moderate	F71

Clinical Code Description	ICD-10
Intellectual Disability -Severe	F72
Intellectual Disability -Profound	F73
Other Intellectual Disability	F78
Unspecified Intellectual Disability	F79
Specific developmental disorders of speech and language	F80
Specific developmental disorders of scholastic skills	F81
Mixed specific developmental disorders	F83
Childhood autism	F84.0
Atypical autism	F84.1
Other childhood disintegrative disorder	F84.3
Asperger syndrome	F84.5
Other pervasive developmental disorders	F84.8
Pervasive developmental disorder, unspecified	F84.9
Other disorders of psychological development	F88
Unspecified disorder of psychological development	F89

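### Sensitivity analysis 5 asks whether the two comparator drugs differ, but it only sets valproate against each one and gives no interval for the difference between them

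*Protocol*

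**What the plan says.** The primary analysis (Protocol 9.7.3.2.1) estimates the valproate HR "compared to the reference group comprised of offspring paternally exposed to lamotrigine or levetiracetam (composite monotherapy) in the same time period". The CM analysis (9.7.3.2.2) pools the two drugs in the same way.

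Item 5 of section 9.7.5 is titled "Simple pairwise comparison valproate vs lamotrigine and valproate vs levetiracetam in monotherapy". It gives reasons why the two comparators may not be interchangeable: different epilepsy types, possible use of lamotrigine but not levetiracetam in bipolar disorder, and different licensing periods. It then sets the aim: "With the objective to evaluate if there is a differential effect of using one or the other comparator".

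The listed work is a description of characteristics (a) and four contrasts. For NDD, valproate is "compared to lamotrigine (monotherapy) treatment at the time of conception" in b and "compared to levetiracetam (monotherapy) treatment at the time of conception" in c. Items d and e repeat this for CM in Norway and Denmark. Item 5 lists no contrast between the two comparators and gives no rule for judging whether the paired results agree.

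**The concern.** The aim concerns a difference between comparators. The null hypotheses of b to e are that valproate equals lamotrigine and that valproate equals levetiracetam, and neither is the null that the aim implies. A reader left with two HRs and two intervals has a point estimate of the difference (the ratio of the HRs) but no valid statement of its uncertainty. The natural shortcut is to see whether both contrasts reach significance, and that answers another question.

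At stake is how the composite reference group is interpreted. The protocol itself doubts that the two drugs are exchangeable, and item 5 is its one comparative outcome analysis aimed at that doubt.

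**Working it through.** **Is the gap filled elsewhere?** The two drugs appear separately in three other places.
- Section 9.7.2.2 presents incidence for "lamotrigine/ levetiracetam (composite and separately) in monotherapy 3 months prior to LMP2". This is descriptive and unadjusted.
- Section 9.7.3.1 compares the exposure groups on covariates, not on outcome risk between the comparators.
- Item 10 of 9.7.5 runs dose analyses within each drug and says "the results from the three within-exposure group analyses for each outcome will not be comparable".

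None gives an adjusted between-comparator estimate with an interval.

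**Inputs.** From section 9.5: NDD reference risk 4%, HR 2.0, two-sided 5%, 80% power, 589 per group (1,178 in total), and a pooled valproate projection of 4,080. HR 1.5 is the lower end of the effect range assumed there. My assumptions: a comparator group as large as the valproate group (9.5 says this only for CM), equal true risk in both comparators, and a lamotrigine share of 50 to 80%.

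**The plan's own figure.** For 4% versus 8%, the smallest n per group with 2n[asin√(0.08 − 1/2n) − asin√(0.04 + 1/2n)]² ≥ (1.96 + 0.842)² is 589, so 1,178 is reproduced.

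**Model.** With d the expected events in a group, each valproate contrast has SE = √(1/d_V + 1/d_comp). The two z statistics have correlation (1/d_V)/(SE₁·SE₂), because they share the valproate group. The chance that exactly one is significant is P₁ + P₂ − 2·P(both).

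**Example: 589 per group, HR 2.0.**
- 50:50 split. d_V = 589 × 0.08 = 47.1 and each comparator has 294.5 × 0.04 = 11.8 events. SE = √(0.0212 + 0.0849) = 0.326 for both contrasts, power is 57% each, correlation is 0.20, and exactly one is significant 43% of the time.
- 80:20 split. The comparators have 18.8 and 4.7 events, the SEs are 0.273 and 0.483, power is 72% and 30%, and exactly one is significant 55% of the time.

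| Per group, HR | 50:50 | 70:30 | 80:20 |
|---|---|---|---|
| 589, HR 2.0 | 43% | 48% | 55% |
| 4,080, HR 1.5 | 18% | 27% | 41% |
| 4,080, HR 2.0 | 0.0% | 0.5% | 3.5% |

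With binomial variances, (1 − p)/(np), the ranges are 43 to 56%, 16 to 39% and 0 to 2.9%.

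**Why two intervals are not enough.** In this simple model the valproate term cancels in the ratio of the two HRs, leaving SE = √(1/d_LTG + 1/d_LEV). At 589 per group, 50:50, that is √(0.0849 + 0.0849) = 0.412, a 95% CI factor of exp(1.96 × 0.412) = 2.24. Treating the two contrasts as independent gives √(0.326² + 0.326²) = 0.461 and a factor of 2.47. The correct width needs the covariance, which the two reported intervals do not carry. Propensity weighting and father clustering make it harder still to recover.

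**Precision of the missing contrast.** Over splits of 50:50 to 80:20, the 95% CI factor is 2.24 to 2.74 with 589 comparator offspring and 1.36 to 1.47 with 4,080.

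**The case against.** The best defence is that item 5 asks something simpler: does the valproate estimate move when the comparator changes? Items b to e show that directly, the analysis is labelled supplementary, and the ratio of the two point estimates can be read off. Section 9.5 says uncertainty will be expressed through confidence intervals, so nothing commits the sponsor to comparing p-values. Incidence for each comparator will also be visible side by side. All of this stands, and it limits the severity. It still supplies no interval for the movement, and the side-by-side incidence is unadjusted although item 5 itself expects the treated populations to differ systematically.

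Two stronger readings are tempting and not supported.
- A reader might infer that unequal group sizes alone will make the two results disagree. The protocol gives no lamotrigine or levetiracetam numbers. Unequal size changes precision and does not systematically shift the point estimates. Disagreement in significance is already 43% at an equal split with 589 per group, and almost vanishes at the pooled size with HR 2.0.
- A reader might infer that a true difference between the comparators would usually be hidden because both contrasts come out significant. How often that happens depends on the valproate risk assumed for such a case, which the protocol does not fix, so no figure can be attached to it.

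A further fair point is that the added contrast is weak within one country, and section 9.7.6 describes pooling for the main outcome results, not for item 5.

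**Conclusion.** The point holds as a mismatch between a stated aim and the contrasts listed for it. No planned analysis estimates the between-comparator difference with a confidence interval, and the shared valproate group means the reported intervals cannot supply one. Comparing significance would be unreliable at the minimum size (43 to 55% discordance with HR 2.0) and at the pooled size with a smaller effect (18 to 41% with HR 1.5), but hardly at the pooled size with HR 2.0 (0 to 3.5%). These figures measure the risk of a reading that the protocol does not prescribe. They rest on equal 4% comparator risks, an assumed split, equal valproate and comparator totals, and a model without weighting or father clustering, both of which would probably reduce precision further. The change is worth making, but it concerns a supplementary analysis and does not undermine the primary estimate.

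**What to change.** Add to item 5 the levetiracetam versus lamotrigine HR for NDD, and the OR for CM in Norway and Denmark, each with a 95% CI. Alternatively, report the ratio of the two valproate HRs (or ORs) with a CI that allows for the shared valproate group and for father clustering, for example by resampling fathers and refitting both models. Three-group propensity weights are not required. Give the result by country and pooled where feasible. State that a difference in significance between b and c, or between d and e, will not be read as a differential effect.

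The cost is one extra contrast from data already in the analysis set. The price is visible imprecision: a 95% CI factor of about 2.2 to 2.7 with 589 comparator offspring, against about 1.4 to 1.5 with 4,080. The report should show this, so that a wide interval around 1 is not taken as evidence that the two drugs are interchangeable.

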**Table 4: Potential confounding variables by outcome**

Outcome	Father
NDD, including ASD	
 
• Age
 
• Bipolar Affective Disorder and mania (ever)
 
• Calendar year of conception of offspring
 

CM	
 
• Age
 
• Calendar year of conception of offspring
 

NDD: Neurodevelopmental disorders; ASD: Autism Spectrum Disorder; CM: Congenital Malformations

**Paternal age.** Multiple epidemiological studies suggest a relationship between advanced paternal age at conception, and adverse neurodevelopmental outcomes (19,20) and congenital malformations (21–23) in offspring. This has been particularly noted with regard to increased risk for autism. ‘Paternal Age’ will be considered a confounding variable a priori, for both outcomes.

**Paternal Bipolar Affective Disorder and Mania.** Valproate is indicated in the treatment of epilepsy, mania and migraine (24). Moreover, children of parents diagnosed with mood disorders including mania have been shown to present with increased risk of neurodevelopmental outcomes. For these reasons, in this study, paternal bipolar affective disorder and mania will be considered as potentially confounding the effect of paternal valproate use on the development of neurodevelopmental disorders in offspring.

**Maternal epilepsy.** There is an increased risk of NDD, including ASD, and CM, in the offspring of female patients with epilepsy (25,26). However the high risk of NDD, including ASD in the offspring of female patients with epilepsy may be due to foetal exposure to AED medication in utero (2), including valproic acid. Offspring from women with epilepsy will only be included in the descriptive analyses of the sample from source population following data extraction, and excluded from the comparative, sensitivity and exploratory objective analyses.

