Paternal polypharmacy would be a potential confounding variable included in the PS for NDD analysis. Maternal polypharmacy would be considered as a risk factor. For the child, polypharmacy after birth will not be considered as a risk factor in this study. This is because of the high potential of reverse causality; for example there is evidence that children with aberrant behaviours irrespective of diagnosis of NDD are more likely to receive psychotropic polypharmacy. Published literature also suggests subjects with ASD may also have comorbid psychiatric conditions requiring psychotropic treatment and in this regard it is not always possible to define temporality (27–29).

For the CM analysis the polypharmacy score will not be calculated because offspring whose parents were exposed to teratogens (risk factor when considered as maternal exposure and confounders when considered as paternal exposure), associated with maternal exposure in the literature, were already excluded from the CM cohort for the purpose of the comparative analyses (see section 9.3.3.2).

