The process is as follows: All potential confounders (section 9.3.3), as reported in literature, will be considered for inclusion in each PS model (39). Also, variables that are unrelated to the exposure but related to the outcome (section 9.3.3) will be included in the PS model. The inclusion of these variables will increase the precision of the estimated exposure effect without increasing bias. In contrast, including variables that are related to the exposure but not the outcome can decrease the precision of the estimated exposure effect without decreasing bias (39). Candidate covariates will be considered to enter the model if the OR or relative risk in a single association with the outcome is higher than 1.1 or lower than 0.9. In order to model the PS for the analysis of each of the two outcomes, three model approaches will be used and compared. The first approach will consist of a logistic regression model with all potential confounders associated with the outcome. Continuous covariates will be modelled using restricted cubic splines as they not only allow for non-linearity, but are also associated with superior model fit at the tails of distributions (40). An attempt to prevent overfitting will be made by specifying 4 knots at 5, 35, 65 and 95% based on Harrell's recommended percentiles (41). Additionally, two-way interactions will be included only for variables which have been identified by a clinician as clinically meaningful. The second modelling approach will be the use of a random decision forest model (42). The advantage of this approach is that interactions between covariates are by definition incorporated into the model and strong predictors and interactions can thus be identified. The random forest model extends easily to multiple outcomes. Finally, the third modelling approach will be a logistic regression informed by the random forest model. In this approach, data-driven identification of interactions as identified by the random forest model will be incorporated into the logistic regression model.

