Once the propensity scores are estimated (separately for the primary and secondary outcome cohorts) they will then be used as weights in the inverse probability of treatment weights approach to balance differences in covariate distribution between offspring paternally exposed to valproate and offspring paternally exposed to lamotrigine/levetiracetam in the adjusted analyses. PS weighting will be used instead of matching for increased generalisability and to avoid the exclusion of patients from the adjusted analyses due to lack of matches (43–46); this is deemed as particularly important in situations where the outcome of interest is relatively rare or infrequent.

For each PS model, the distributions of estimated propensity scores will be visually compared across the three models, separately for the primary and secondary outcome. Selection of the best models for the primary and secondary outcome cohorts will be based on the balance achieved in the weighted exposure groups after using inverse probability of treatment weights. Only the best PS models for the primary and secondary outcome cohorts will then be used to apply inverse probability of treatment weights in the multivariate analysis.

The best PS modelling approach might not be the same for the two cohorts, and similarly the covariates included in the PS model will differ as the two outcomes have different risk factors and confounders.

A sensitivity analysis to compare the results from the PS-weighted approach with the traditional approach of covariate adjustment will be performed, as reported in section 9.7.5, for both primary and secondary composite outcomes, using the composite lamotrigine/levetiracetam monotherapy comparator.

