6. *Comparison of the PS-weighted model with the traditional covariate adjustment model:* A Cox PH regression model will be used to estimate the HR of NDD, including ASD, with 95% CI (using offspring's calendar age in years as the underlying timescale) in offspring paternally exposed to valproate monotherapy within 3 months prior to LMP2 date compared to the reference group comprised of offspring paternally exposed to lamotrigine or levetiracetam (composite monotherapy) in the same time period. A logistic regression model will be used to estimate the OR of CM with 95% CI in offspring paternally exposed to valproate monotherapy within 3 months prior to LMP2 date compared to the reference group comprised of offspring paternally exposed to lamotrigine or levetiracetam (composite monotherapy) in the same time period. The list of confounders to be included is reported in Table 4. Within-family dependencies introduced by multiple offspring per father will be accounted for using sandwich estimators. Different results are expected because two different set of variables will be used for the adjustment due to the inclusion of risk factors in the PS model to improve efficiency; (c) noncollapsibility of the two models (46,50–52) (“the conditional OR or HR does not equal the marginal OR or HR in the presence of non-null treatment effect, even in the absence of confounding and effect modification” (52)).
7. *Effect of paternal exposure to valproate on NDD in offspring exposed and unexposed to AEDs after birth, and/or diagnosed with epilepsy.* As reported in section 9.3.3.1 the neurodevelopmental effects of postnatal exposure to AEDs and/or diagnosis of epilepsy on risk of NDD are not completely understood. Therefore, in the primary analysis such children are excluded. A sensitivity analysis will be conducted to explore the impact on the risk of NDD, including ASD, in offspring paternally exposed to valproate (monotherapy), compared to lamotrigine or levetiracetam (composite monotherapy) treatment at the time of conception will be performed by including these offspring. Offspring exposure to AEDs and diagnosis of epilepsy between birth and the exit date will each be considered time dependent, and thus allowed to take place at any time during the follow-up period. However, after the first dispensation of AEDs, the offspring will be considered exposed until the exit date.

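### Sensitivity analysis 6 changes the covariate set along with the adjustment method, and for NDD its set leaves out paternal polypharmacy, so a gap from the weighted result cannot be traced to the weighting

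*Protocol*

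**What the plan says.** Section 9.7.3.2.3 gives the purpose: "A sensitivity analysis to compare the results from the PS-weighted approach with the traditional approach of covariate adjustment will be performed", for both composite outcomes.

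Section 9.7.5, item 6, fixes the adjusted Cox model (NDD) and logistic model (CM): "The list of confounders to be included is reported in Table 4". Table 4 lists paternal age, paternal bipolar disorder or mania, and calendar year of conception for NDD. For CM it lists paternal age and calendar year.

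The propensity score (PS) is built from a wider pool. Section 9.7.3.2.3 states: "All potential confounders (section 9.3.3), as reported in literature, will be considered for inclusion in each PS model". It adds that "variables that are unrelated to the exposure but related to the outcome (section 9.3.3) will be included in the PS model". Candidates must also pass a screen on their single association with the outcome (ratio above 1.1 or below 0.9).

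On co-medication, the text of section 9.3.3 after Table 4 says: "Paternal polypharmacy would be a potential confounding variable included in the PS for NDD analysis". The footnote to Table 2 likewise says that co-medication will be adjusted for through a polypharmacy index. The same part of section 9.3.3 says that the index is not calculated for CM.

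Item 6 anticipates disagreement: "Different results are expected because two different set of variables will be used for the adjustment". The reasons it gives are that risk factors enter the PS for efficiency, and that the two models are noncollapsible.

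**The concern.** A comparison of two adjustment methods is informative when the method is the only thing that changes. Here the covariate set changes as well, and for NDD one variable that drops out is a confounder by the protocol's own description. Suppose the weighted hazard ratio (HR) and the adjusted HR differ. The reader cannot tell whether a few large weights drive the weighted estimate, whether a model is misspecified, or whether the second model is simply less adjusted. The advance statement that results will differ makes any gap easy to set aside. If the two HRs agree, the fuller adjustment may have made little difference or opposing effects may have cancelled.

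This matters because item 6 is the only planned comparison of the weighted effect estimate with a different adjustment method. Balance diagnostics are planned, but good average balance does not show how far the estimate depends on a small number of heavily weighted offspring.

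**Working it through.** **1. The covariate sets side by side**

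| | Adjusted model, item 6 (Table 4) | PS candidates (section 9.3.3) |
|---|---|---|
| NDD | paternal age, bipolar/mania, calendar year (3) | those 3, the paternal polypharmacy index, and the Table 2 entries (13 maternal, 6 paternal, 7 offspring) |
| CM | paternal age, calendar year (2) | those 2 and the Table 3 entries (13 maternal, 0 paternal, 6 offspring); no polypharmacy index |

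The right-hand column lists candidates. The 1.1/0.9 screen, data availability and model fit decide what stays.

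**2. Do the protocol's two reasons account for a gap?**

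*Efficiency variables.* Section 9.7.3.2.3 says that variables related to the outcome but not to exposure improve precision without adding bias. Leaving them out should not shift the estimate systematically, apart from noncollapsibility. The polypharmacy index is not in that class, because section 9.3.3 calls it a potential confounder. Item 6 does not mention that it is missing.

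*Noncollapsibility.* The inputs from section 9.5 are a 4% reference risk of NDD and an HR of 2.0. They belong to the plan's own sample size, which reproduces with the Freedman formula at two-sided 5% and 80% power: (1.96 + 0.8416)² × [(2 + 1)/(2 − 1)]² / [(0.04 + 0.08)/2] = 7.849 × 9 / 0.06 = 1177.3, against 1178 stated.

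Assume one binary covariate with prevalence p = 0.30 in both groups (so no confounding), covariate hazard ratio c, and conditional exposure HR 2.0. Solve for the baseline cumulative hazard m in

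1 − [(1 − p)e^(−m) + p·e^(−cm)] = 0.04,

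then replace m by 2m for the exposed risk r1. The marginal HR is ln(1 − r1) / ln(1 − 0.04).

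For c = 3: m = 0.0257, r1 = 0.0779, marginal HR = −0.0811 / −0.0408 = 1.987.

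| Reference risk | c = 1.5 | c = 2 | c = 3 |
|---|---|---|---|
| 4% | 1.998 | 1.995 | 1.987 |
| 10% | 1.996 | 1.987 | 1.966 |

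The gap from 2.0 is under 1% at 4% risk and under 2% at 10%.

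**3. What could one omitted confounder do?**

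The Bross formula for a binary confounder with prevalence P1 in the valproate group, P0 in the comparator group and risk ratio RR gives the factor

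[1 + P1(RR − 1)] / [1 + P0(RR − 1)].

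The protocol gives no values for these, so all of them are assumed:

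| P1 v P0 | RR 1.2 | RR 1.5 | RR 2.0 |
|---|---|---|---|
| 0.40 v 0.30 | 1.019 | 1.043 | 1.077 |
| 0.45 v 0.30 | 1.028 | 1.065 | 1.115 |
| 0.50 v 0.25 | 1.048 | 1.111 | 1.200 |
| 0.20 v 0.35 | 0.972 | 0.936 | 0.889 |

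For example, 0.50 v 0.25 with RR 2.0 gives 1.50/1.25 = 1.20. The index itself is a count, so the binary case is only an illustration.

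**4. Reading the two together**

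Under these assumptions, a gap of more than 1 to 2% beyond sampling error is not explained by noncollapsibility. It would come from the covariate set, from the weights or from model specification. Item 6 as written cannot separate these.

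**The case against.** Several objections have force.

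- *A short regression on pre-specified confounders is a legitimate sensitivity analysis.* It is, and it tests robustness to the covariate set. At the planned size there would be about 589 × 0.04 + 589 × 0.08 = 70.7 events, too few for all 26 Table 2 entries in an ordinary Cox model. This supports keeping the Table 4 model as one row. It does not make that model a comparison of methods, which is the stated purpose.
- *The protocol discloses the different sets.* True. It does not disclose that a named confounder, and not only efficiency variables, is left out. The reasons in item 6 also carry a label (c) without (a) or (b), so part of the explanation may be lost. The point rests only on the text that remains.
- *Polypharmacy could be screened out of the PS.* Possible. Using the final PS covariates in both models deals with that automatically.

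A reader might also infer more than the documents support:

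- *That item 6 is the only check on the weighting.* Section 9.7.3.2.3 plans a visual comparison of PS distributions and chooses the PS model on the balance achieved after weighting.
- *That the confounder omission affects CM.* The index is not calculated there, and the father column of Table 3 is empty.
- *That paternal affective, neurotic, psychotic and substance-use disorders are dropped confounders.* The protocol classes them as risk factors in Table 2. One may dispute that, but it is not a contradiction in the text.
- *That agreement would mean nothing.* Close agreement is weak reassurance.

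**Conclusion.** The point holds in limited form. Item 6 compares methods while also changing covariates, so a difference cannot be attributed to the weighting. For NDD there is also an internal inconsistency: section 9.3.3 and the Table 2 footnote treat paternal polypharmacy as something to adjust for, and Table 4, and hence item 6, omits it. For CM only the difference in sets remains, through whatever Table 3 risk factors enter the PS.

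It is tempting to say that the Table 4 model will be biased upwards by a large amount. The documents do not support this. They give neither the distribution of co-medication by drug group nor its association with NDD, so size and direction are both open. The range of about 0.89 to 1.20 depends entirely on the assumed prevalences and risk ratios. The figure of under 1% for noncollapsibility uses the plan's 4% and 2.0, with an assumed covariate prevalence of 30% and covariate hazard ratio of 1.5 to 3. The primary analysis itself is not affected.

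**What to change.** 1. In section 9.7.5, item 6, replace the reference to Table 4 by the same pre-conception covariates as in the final PS model of that cohort. If the final PS model holds any variable measured later, state how it is handled, so that the two sets can still be matched.
2. Where a country has few events, use a penalised fit or adjust for a spline of the logit of the PS. The spline version shares any fault in the PS model, so it tests the weighting only.
3. Keep the Table 4 model as a separate row labelled as minimal adjustment.
4. Add the paternal polypharmacy index to the NDD row of Table 4, so that it agrees with section 9.3.3.
5. Revise the sentence on expected differences to fit the matched comparison.

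There is a precedent in the protocol: item 10c of section 9.7.5 already carries covariates over from the final models of the primary comparison. The cost is a wording change, one more model per outcome and country, and a slightly wider confidence interval where events are few.
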